3. SYNOPSIS

Title	Virus shedding and environmental deposition of novel A(H1N1) pandemic influenza virus						
Short title	Virus shedding in novel influenza A(H1N1)						
Chief Investigator	[name]						
Objectives	The objectives of the proposed study are:						
	Primary:						
	 To determine the quantity of infectious virus present in the nose, on surfaces, in the air and in stool, according to time from symptom onset, symptom constellation (e.g. presence of cough or sneeze), distance from source and particle size (in air); To correlate serial virus shedding in pandemic influenza patients against data on near-patient environmental contamination (surfaces and air). 						
	Secondary:						
	 To describe virus shedding (quantity of infectious virus) and duration according to important patient sub-groups, notably adults and children, those with mild illness (community patients) and those with more severe disease (hospitalised patients). To determine if aerosol generating procedures (most likely to be performed on ITU) are associated with changes in the quantity of environmental contamination with live virus, either in relation to quantity or particle size, or distance from source. To investigate the possibility of estimating the number of influenza-infected individuals in an area by the quantity of influenza virus recovered in sewage influent. 						
	Policy related (to provide scientific data suitable for policy refinement on):						
	Safety distances' around patients with pandemic and seasonal influenza.						
	 Appropriate use of respiratory personal protective equipment (RPPE) and infection control practices for pandemic and seasonal influenza, according to patient type, illness severity and time since symptom onset. 						
	 Antiviral treatment duration for patients with pandemic influenza. To develop an alternative surveillance strategy for quantifying influenza infections in a community. 						

Study Configuration	Multi-centre, observational + interventional
Setting	Community and Hospital

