The Centre for Ecology & Hydrology will be dedicated to using the viral shedding data from stools to inform a model which is being generated to predict the number of influenza-infected people within a geographic area based on the quantity of influenza virus recovered in sewage

influent. This generic approach is already in use by the WHO to assess polio infections/immunizations in an area. It is our aim to test whether sewage influent can serve as a medium for estimating (pandemic) influenza-infected individuals within a region. We believe that if this study can demonstrate that there is a predictable amount of viral shedding in the stool of influenza-infected patients, the sewage-based epidemiology screening approach could be used as an early detection tool for the spread of pandemic influenza within an area.

Existing Research:

Virus Shedding:

To our knowledge no data are yet available publicly on the kinetics of virus shedding in patients with novel influenza A (H1N1). However, confidential data obtained from diagnostic specimens by the Health Protection Agency suggest that the duration of shedding may be slightly longer than with seasonal influenza and up to 8 days in some patients. However these data derive from semi-quantitative PCR readings and so relate to the detection of swine virus specific nucleic acid but not to the presence of infectious virus. In addition, the data are cross-sectional, i.e. pooled from single samples taken from individuals at different time points in their illnesses as opposed to serial measurements from the same individuals (*[name]: personal communication; confidential unpublished data*). Most data are from schoolchildren in whom the duration of shedding tends to be longer than in adults in any case. Until data become available from studies such as the one we propose, the estimated duration of influenza virus shedding is based upon previous experience with seasonal influenza virus infection.

The period of viral shedding can be inferred from the length of time that virus can be recovered from respiratory secretions and is influenced by age of the person infected, level of immune competence and treatment with antiviral agents. It may also be influenced by symptom severity and fever (both proxies for virus replication and viral load) or other unknown factors.

Adults;

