Despite the above, the detection of *viable* virus in aerosols generated by humans has not been shown before (as far as we know). The generation of information about the presence of viable influenza virus in the environment will be fundamental to our understanding of the routes of transmission. With this in mind, we have recently attempted to demonstrate that viable influenza virus can be found in aerosols as part of the Proof of Concept study (ITSDG-01) mentioned earlier. In preparation for this, the University of Nottingham received sampling equipment from CDC/NIOSH (identical to that used by [name] et al above). Prior to its use we approached the Health and Safety Laboratory in England to pilot setting-up of the sampling equipment, calibration and evaluating the utility of the sampler for capturing live influenza. Following experiments that involved aerosolizing influenza virus in a laboratory, live virus could be detected by an air sampler using the virus plaque assay technique (and PCR results were concordant). Following on from this, air sampling recently took place during the proof of concept study – results are awaited. Thus the technique of air sampling using the CDC/NIOSH equipment has been validated in the UK at the Health and Safety Laboratory and (pending results) during a quarantine based challenge study.

Research at CEH has already demonstrated in preliminary research the capacity of the influenza virus to persist in sewage influent for over 2 hours with only a 60% loss in total counts (quantitative PCR). Given that our ability to detect the virus spans >8 orders of magnitude using quantitative PCR, a 60% decline is negligible (e.g., lowering virus counts from 5.0 x 10^6 to 2.0 x 10^6). Hence, there is every reason to expect that if the virus is being shed by influenza-infected patients, the virus should be recoverable in the sewage influent.

6. Research Objectives

The objectives of the proposed study are:

Primary:

- To determine the quantity of infectious virus present in the nose, on surfaces, in air and in stools, according to time from symptom onset, symptom constellation (e.g. presence of cough or sneeze), distance from source and particle size (in air);
- ii) To correlate serial virus shedding in pandemic influenza patients against data on near-patient environmental contamination (surfaces and air).

Secondary:

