- Hospitalised adults: 4 patients, 4 sampling days (sampling every other day for 8 days), 6 samples each time (3 from each sampler) = 96
- Hospitalised children: 4 patients, 6 sampling days (sampling every other day for 12 days), 6 samples each time (3 from each sampler) = 144
- Adults in their own homes: 4 patients, 4 sampling days (sampling every other day for 8 days), 6 samples each time (3 from each sampler) = 96
- Children in their own homes: 4 patients, 6 sampling days (sampling every other day for 12 days), 6 samples each time (3 from each sampler) = 144

A sample patient schedule can be seen at appendix 2.

4. Stool Sample Collection

Detailed instructions will be provided explaining how to obtain a sample. We will ask the patient to empty their bladder first if possible. They will then place a collecting plate in the toilet bowl which will catch the stool. A sample can then be taken and put in the container. The remaining stool is then tipped into the toilet and flushed away. The plate is disposed of in a rubbish bag. Once the sample container has been securely capped, it should be placed in a specimen bag and kept in a small cooler box (which will be provided). Hand washing / hygiene measures will be stressed. Stool samples will be collected daily along with the other samples.

Sample Processing (stool samples dealt with separately – see below)

The generation of \approx 3,300 samples for both PCR and PA is a considerable amount of work requiring not just expertise but also significant laboratory resources, including time. Thus, it is not possible to generate results on all samples collected in a short period. We therefore propose to define a sample processing protocol based on results from the first few cases. It could include the following;

- If a patient tests negative for swine flu (as part of NHS care) we will exclude them from further study.
- Environmental swabs will not be processed if nasal swabs from a case are PCR negative.
- Environmental swabs will only be processed if nasal swabs from a case show a high viral load.
- Environmental swabs will not be processed for PA if nasal swabs from a case are PA negative.

Note; samples that are not processed rapidly will be retained for analysis in the future should this be of interest.

Transport and storage of participant samples

Transport

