Samples will be analysed using real-time quantitative PCR and/or plaque assay (PA quantification of infectious virus present in the sample). Upon defrosting prior to testing, samples will be split for PCR (refrozen) to detect genome and culture to detect viable virus. The PCR assay is a modification of the real-time quadriplex PCR assay for the detection of influenza (VSOP 25) issued by the Standards Unit, Health Protection Agency, Centre for Infections, Colindale, London. The assay will be performed following good laboratory practice, by trained individuals. Appropriate controls, both negative and positive will be included in each run. All machinery and laboratory equipment is maintained to clinical standards by the East of England Regional Health Protection Laboratory. The plaque assays are performed in the Division of Virology, Department of Pathology, University of Cambridge, following a risk assessed procedure. The laboratories are maintained by the University and are regularly inspected. Both PCR and plaque assays will be performed by trained biomedical scientists.

[figure not shown]
Stool sample processing

Centre for Ecology & Hydrology will process samples using the same PCR methods as determined by [name]. Stool samples will be stored in a -80C freezer located at the Centre for Ecology & Hydrology, Oxford, [name]. Samples will be identifiable through participant study codes and date of birth, as per the nasal swab samples. Following analysis, all samples will be destroyed. Analysis is expected to be complete by February 2010.

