In a third stage, a Generalized Linear Model with random effects will be used to determine the key predictors for the quantity of infectious virus in surfaces and in the air. A survival analysis will also be implemented to assess the key predictors for the duration of viral shedding.

Outcome Measures

- 1. Virus shedding and deposition as measured by virus culture and quantitative PCR. (Quantitative PCR and plaque assay of respiratory virus specimens (nasal swabs) from patients and surfaces and air around them). Virus shedding and deposition as measured by virus culture and quantitative PCR.
- 2. Daily symptom scores and patient temperature readings
- 3. Medication logs
- 4. Household/ward daily temperature and humidity logs

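### Primary objective (i) promises the quantity of infectious virus in stool, but the only assay named for stool is PCR, which detects genome and not viable virus

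*Protocol*

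**What the plan says.** The promise appears twice. Section 6 gives the first primary objective as "To determine the quantity of infectious virus present in the nose, on surfaces, in air and in stools", and the Synopsis has "To determine the quantity of infectious virus present in the nose, on surfaces, in the air and in stool". The quantity to be measured is infectious virus, and stool is one of four named sources.

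The assays are set out in Section 10. For the main samples, the Protocol describes "plaque assay (PA quantification of infectious virus present in the sample" as the method for infectious virus and says that "samples will be split for PCR (refrozen) to detect genome and culture to detect viable virus". Stool is taken out of this workflow by the heading "Sample Processing (stool samples dealt with separately – see below". The later stool paragraph says that the "Centre for Ecology & Hydrology will process samples using the same PCR methods as determined by" a named colleague; it mentions no culture or plaque assay. Culture is assigned to the Cambridge virology laboratory, and no transfer of stool to that laboratory is described.

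Section 11 (Outcome Measures) and the Synopsis open the first outcome with general wording about shedding and deposition by culture and quantitative PCR. They then specify "Quantitative PCR and plaque assay of respiratory virus specimens (nasal swabs) from patients and surfaces and air around them". Stool is not among the specimens listed there.

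**The concern.** A primary objective should be answerable with the measurements planned. Here the objective asks for infectious virus in stool and the named stool assay returns nucleic acid.

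The Protocol treats this difference as important. In Section 5 (Virus Shedding) it qualifies existing swine flu data because they "relate to the detection of swine virus specific nucleic acid but not to the presence of infectious virus". In the same section, on adults, it says that PCR can still find virus after the usual five days, when culture is usually negative.

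At stake is how a PCR-positive stool will be labelled. Reported under objective (i) as worded, it would stand as a quantity of infectious virus when infectivity had not been measured.

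**Working it through.** **1. Objective against assay.**

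| Source | Named in objective (i) as infectious virus | Assay named in Section 10 |
|---|---|---|
| Nose | Yes | PCR and/or plaque assay |
| Surfaces | Yes | PCR and/or plaque assay, possibly conditional on nasal results |
| Air | Yes | PCR and/or plaque assay |
| Stool | Yes | PCR; nothing else named |

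By the Protocol's own definitions, only culture or plaque assay yields infectious virus. For stool, no such assay is named.

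**2. Is stool in the plaque-assay workload?** Section 10 gives about 3,300 samples for both PCR and plaque assay. Rebuilding this from the Section 10 counts:

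- Nasal: 200 + 275 + 200 + 275 = 950
- Surface: 150 + 225 + 600 + 900 = 1,875
- Air: 96 + 144 + 96 + 144 = 480
- Total: 950 + 1,875 + 480 = 3,305

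The stated figure is reproduced without any stool.

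**3. What would the total be with stool?** The Synopsis plans about 20 stool patients, with a roughly equal mix of adults and children, and Section 10 says stool is collected daily. The Protocol gives no stool sample count. I therefore assume 10 adults and 10 children, and take the day counts from Section 10 (nasal swabs) and the Synopsis (maximum duration):

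| Days, adult / child | Stool samples | Total with stool | Excess over 3,300 |
|---|---|---|---|
| 8 / 10 | 10×8 + 10×10 = 180 | 3,305 + 180 = 3,485 | 185/3,300 = 5.6% |
| 8 / 11 | 10×8 + 10×11 = 190 | 3,305 + 190 = 3,495 | 195/3,300 = 5.9% |
| 10 / 12 | 10×10 + 10×12 = 220 | 3,305 + 220 = 3,525 | 225/3,300 = 6.8% |

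The total without stool is within 5 samples of the stated figure; the totals with stool exceed it by 185 to 225. The count agrees with the text: stool lies outside the PCR and plaque-assay workload.

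**The case against.** The best counter-argument is that PCR-only testing is inferred from silence. The stool paragraph never says that PCR is the sole method, a figure just before it is not shown, and the sample count proves only that stool is outside the main tally, not that no stool culture was intended. This stands as a caution. But the separate handling, the single named method, the listed specimens and the count all point the same way, and nothing in the text points to a stool culture.

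A second argument limits the consequence. Later in Section 6 the primary objective is restated as relating virus in the nose to the environment, time since onset and severity; stool comes in afterwards, to supply the sewage model. Stool is optional in Appendix 2 and limited to a sub-study. This stands too: the defect is confined to one specimen in one objective.

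Some stronger readings are tempting, but the Protocol does not support them:

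- A reader might infer that all nose, surface and air samples receive both assays. Section 10 says PCR and/or plaque assay, and lists possible rules under which environmental swabs go unprocessed.
- A reader might infer that stool is wholly absent from the outcome measures. The general first sentence could cover it; only the listed specimens omit it.
- A reader might take the destruction of stool samples after analysis as a special obstacle. The same is said of the main samples.
- A reader might take the Section 5 remark on nucleic acid as a verdict on this study's PCR. It describes another body's semi-quantitative data. The Section 10 definitions and the Section 5 statement on PCR outlasting culture are the firmer support.

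**Conclusion.** The point holds for the stool component of primary objective (i). As written, that component cannot be answered, because the one assay named for stool does not measure what the objective names. An analysis plan could not repair this, since infectivity cannot be derived from a PCR result.

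It affects all stool data: about 20 patients and roughly 180 to 220 samples, under the assumptions of a 10/10 adult and child split and complete daily collection. It also rests on reading the stool paragraph as complete, which is the natural reading.

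It would be wrong to conclude that the primary objective as a whole fails. The nose, surface and air components, and the stated sample size, are unaffected.

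**What to change.** In Section 6 and the Synopsis, take stool out of the infectious-virus wording of objective (i) and state its component as the quantity and duration of influenza viral RNA in stool by quantitative PCR. In the outcome measures (Section 11 and Synopsis), name stool RNA explicitly, so that PCR-positive stool is not reported as infectious virus.

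This is rewording and needs no extra assays. It has one small cost: the study then makes no claim about faecal infectivity, although Section 5 links the kinetics of faecal shedding to the likely infectious period. The sewage model is unaffected because it relies on PCR counts. If the sponsor wants to keep the infectivity question, the alternative is to add a stool culture or plaque assay to the laboratory section and the outcome measures, which would add laboratory work.

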A virus can get on to a surface in a number of ways (e.g. indirectly via touch and droplets of any size settling out), but which surfaces (both in terms of proximity to the patient and physical nature) are commonly contaminated and how long virus remains viable for are uncertain. A virus can also become airborne and transmit through this route (inhalation and direct impaction of droplet nuclei on mucous membranes). The proposed research will evaluate the relative hazard of the touched environment versus the respired environment. In doing this it will provide a policy steer towards interventions that are likely to be important in reducing transmission. For example; if the touched environment is associated with much higher quantities of viable virus than the respired environment then hand hygiene and surface cleaning advice needs greater emphasis; but conversely if the respired environment is more important, strengthening PPE guidance (particularly around face masks and respirators) or applying 'distance or proximity rules' would be of greater importance.

Where - 'Safety distances' around patients with pandemic and seasonal influenza:

The devices we propose to use for air sampling are not only portable but are also validated and capable of separating out particles into three size ranges. Sampling air within 3 feet and >7 feet away from a patient will inform safety distances. For example;

Healthcare settings;

- If air sampling detects virus only within 3 feet of a patient then we can be confident about need for PPE within 3 feet. If viable virus is detected in the air at greater distances then the standard 3 feet safety distance should be revised; but the need for respirators would depend on the size of particles from which we detect viable virus.
- This may have a significant impact on the care of patients in NHS facilities and the advice given to HCWs regarding the implementation of infection control procedures.

Community;

When a person with a high risk condition (for complications of influenza) resides in a household with an index case, then safety distances around an infected case could be important, potentially helping co-habitees to protect themselves. At the height of the pandemic, it is almost certain that families will have to care for each other as hospital capacity will be saturated. Families need to know the safest procedures to adopt and the government needs to issue this advice.

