A two-stage bio aerosol cyclone sampler will be used to i) measure the quantity of influenza virus and ii) look for live virus in aerosol particles around patients. The sampling devices and accessory equipment have been loaned by NiOSH as previously mentioned and have been validated both in the UK and the US (see picture at appendix 2). The sampler draws in air at 3.5 litres/min and separates particles into three size fractions (>4, 1-4 and <1 micrometers). The particles are collected in falcon conical tubes containing VTM or on filter paper These fraction sizes are important because particles of less than 4 micrometers in diameter (aerosols) are capable of being inhaled and reaching the lower respiratory tract, where as particles >4 micrometers behave as droplets. It would therefore be interesting to know whether influenza, particularly viable influenza can be found in such particles as this would weight to premise that influenza can be transmitted by aerosols. In addition, by placing samplers at specified or consistent distances away from patients we can assess whether larger particles (droplets) can travel more than commonly accepted 4ft distance.

The samplers will run for 3 hours for each collection. They are powered by an air pump which does generate some noise but this is not excessively intrusive. They will be positioned in the following places;

 Hospital setting: One sampler will be placed within 4ft of the patient's bed, at chest height and within a 180 degree angle of the patients face. A further sampler will be placed at a distance of >7ft from the patients bed ideally against the wall opposite the patient, 150cm off the ground. Samplers will be mounted on drip stands.
 If a patient moves out of a side room we will continue nasal swabbing but will stop

If a patient moves out of a side room we will continue nasal swabbing but will stop environmental sampling.

- Household setting: We will only collect samples if we know that a patient will be relatively stationary for the duration of sampling, e.g. in bed. Samplers will be placed as above. Samples will be taken every other day during a patients follow up from the first day. We expect to have the use of 6 sampling devices but because of equipment and time constraints we will

not be able to perform air sampling around every patient. Over the course of the study we will aim to follow 16 patients.

Based on this we expect to obtain 480 samples in total:

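### Finding virus 'only within 3 feet' cannot be established when the near air sampler stands anywhere within 4 ft of the bed, the far one beyond 7 ft, and only 8 hospital patients are sampled

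*Protocol*

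**What the plan says.** Section 6 of the Protocol, under the 'Where' question on safety distances, describes the layout as follows: "Sampling air within 3 feet and >7 feet away from a patient will inform safety distances". Two illustrative inferences for healthcare settings follow. The first is "If air sampling detects virus only within 3 feet of a patient then we can be confident about need for PPE within 3 feet". The second is "If viable virus is detected in the air at greater distances then the standard 3 feet safety distance should be revised", with the need for respirators then depending on particle size.

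Section 10, under Air Particle Collection, gives the positions that staff will actually use. For the near sampler: "One sampler will be placed within 4ft of the patient's bed, at chest height". For the far sampler: "A further sampler will be placed at a distance of >7ft from the patients bed". For households: "Samplers will be placed as above". The same subsection says that the layout will show whether droplets "can travel more than commonly accepted 4ft distance".

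Air sampling is planned for 16 patients, 4 in each of the four groups, so 8 are in hospital. The expected yield is 480 samples.

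**The concern.** The two sections disagree on the near distance (3 feet against 4 ft) and on the point it is measured from (the patient against the bed). A sampler 3.5 ft from the bed complies with Section 10 and does not meet the description in Section 6. This concerns where equipment physically stands, so an analysis plan written later could not repair it.

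The first inference needs two things: a positive that can be located within 3 feet, and absence of virus beyond 3 feet. The layout secures neither, and few patients are sampled.

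Distance from source is part of the first primary objective, and safety distances are a listed policy objective. The Protocol expects the answer to affect patient care in NHS facilities and the advice given to healthcare workers. A null result at the far sampler that was read as absence beyond 3 feet would be the costly error.

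**Working it through.** **1. The two sections side by side.**

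| Item | Section 6 | Section 10 |
|---|---|---|
| Near sampler | within 3 feet | within 4 ft |
| Far sampler | >7 feet | >7 ft |
| Measured from | patient | bed |
| Reference limit | 3 feet | 4 ft |

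The far distance agrees, apart from its reference point. The near distance, the reference point and the limit under test do not.

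**2. What each pattern of results can show.**
- Near positive, far negative: the near sampler may have stood between 3 and 4 ft from the bed, and at a different distance from the patient. The positive cannot be assigned to within 3 feet. Nothing is sampled between about 4 and 7 ft, so virus there would be missed. 'Only within 3 feet' is not established.
- Far positive for viable virus: this meets the second inference whichever near distance is used.
- Both negative: neither inference is triggered.

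The data-collection list in Section 10 names room temperature, humidity, aerosol-generating procedures and nebuliser use. It does not name the actual sampler distance, so as written the plan does not secure the information needed to sort this out afterwards.

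**3. The plan's own count.** Patients × sampling days × 6 samples per session:
- hospitalised adults: 4 × 4 × 6 = 96
- hospitalised children: 4 × 6 × 6 = 144
- adults at home: 4 × 4 × 6 = 96
- children at home: 4 × 6 × 6 = 144

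The total is 480, as stated. Each position has (4×4) + (4×6) + (4×4) + (4×6) = 80 sampler runs, of which 16 + 24 = 40 are in hospital.

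**4. What zero far detections would mean, counted by patient.** For 0 of n, the exact upper 95% limit is 1 − 0.05^(1/n) one-sided and 1 − 0.025^(1/n) two-sided. The 95% level is an assumption, because the Protocol sets none for air sampling.

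| Patients | One-sided | Two-sided |
|---|---|---|
| 8 (hospital) | 31.2% | 36.9% |
| 16 (all) | 17.1% | 20.6% |
| 4 (one group) | 52.7% | 60.2% |

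Put the other way, suppose 10% of patients would show virus beyond 7 ft. The chance that none of 8 does is 0.9^8 = 43.0%, and that none of 16 does is 0.9^16 = 18.5%. At 20%, the chances are 0.8^8 = 16.8% and 0.8^16 = 2.8%.

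**5. Counted by run.** Runs in one patient are correlated. With an average of 80/16 = 5 runs per patient, effective n = runs / (1 + (5 − 1) × ICC). The Protocol gives no ICC, so the whole range is shown, with one-sided upper limits after zero detections:

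| ICC (assumed) | 40 hospital runs | All 80 runs |
|---|---|---|
| 0 | 7.2% | 3.7% |
| 0.5 | 20.1% | 10.6% |
| 1 | 31.2% | 17.1% |

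**The case against.** The strongest reply is that this is not a decision rule. The sentence is introduced as an example, under an objective meant to supply data for policy refinement, and Section 11 contains no 3-foot criterion. Section 11 plans description by distance and a random-effects model for virus quantity in air, and neither depends on the example. That is right, and the point is put here as one about an unsupported inference.

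A reader might go further and infer that the safety-distance question cannot be answered at all. The documents do not support that. Viable virus beyond 7 ft would bear on the 3-foot distance wherever the near sampler stood, and even one such detection would be informative. A reader might also take the sentence to claim confidence that protection is unnecessary further away. It does not: 'confident' attaches to the need for PPE within 3 feet, which rests on a positive near sample. The problem of non-detection reaches only the absence implied by 'only'.

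Three further replies have some force. First, 'within 4ft' permits a position inside 3 feet, and the Background treats 3 to 4 feet as one short-range zone, so a broad near-against-far contrast survives. But permitting a position does not guarantee it, and the inference is specific to 3 feet. Second, serial sampling adds information, and the by-run limits can be much lower than the by-patient ones. That holds only if runs within a patient are close to independent, and a limit per run answers a different question from a limit per patient. Third, the small number is openly explained by equipment and time constraints. That justifies the sample, but not the strength of the inference drawn from it.

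**Conclusion.** The concern holds in this limited form. Sections 6 and 10 contradict each other on the near sampling distance and its reference point. The inference from virus being found 'only within 3 feet' is not supported by either the sampler layout or the number of patients.

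Because the inference is listed under healthcare settings, 8 is the relevant number of patients. Zero far detections would leave up to 31% of patients (one-sided) or 37% (two-sided) compatible with detectable virus beyond 7 ft. Using all 16 gives 17% and 21%. These limits treat patients as independent and describe what this sampling scheme would detect; any virus the samplers miss would weaken a claim of absence further. The band of about 4 to 7 ft stays unobserved whatever the number of patients. The inference from a viable far positive is unaffected.

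**What to change.** - Reconcile Section 6 with the Air Particle Collection text in Section 10, so that both give one near distance and one reference point (patient or bed). The documents do not show which is intended, and this review does not choose.
- Record the actual distance of both samplers from that reference point at every session, and analyse distance as recorded.
- Replace the 'only within 3 feet' inference with a report of the number of patients with detectable virus, and with viable virus, at each sampled distance, with exact 95% limits. Give hospital patients separately where the conclusion concerns healthcare settings.
- State that no conclusion is drawn for the unsampled band of about 4 to 7 ft.

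The cost is one extra recorded field per session and a more modest conclusion. No additional samplers or patients are needed.
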